## SUPPLEMENTS/APPENDICES

### A: Study Schedule

## LIST OF ABBREVIATIONS

AE	Adverse Event
AECOPD	Acute Exacerbation of Chronic Obstructive Pulmonary Disease
ARI	Acute Respiratory Infection
ARLG	Antibacterial Resistance Leadership Group
ATP	According-to-protocol
CFR	Code of Federal Regulations
CLIA	Clinical Laboratory Improvement Amendments
CMS	Clinical Materials Services
COPD	Chronic Obstructive Pulmonary Disease
CRF	Case Report Form
DMID	Division of Microbiology and Infectious Diseases, NIAID, NIH, DHHS
DOOR	Desirability Of Outcome Ranking
DSMB	Data and Safety Monitoring Board
ED	Emergency Department
FDA	Food and Drug Administration
FWA	Federal-Wide Assurance
GCP	Good Clinical Practice
ICH	International Conference on Harmonization
IDES	Internet Data Entry System
IEC	Independent or Institutional Ethics Committee
IRB	Institutional Review Board
ITT	Intention-to-treat
JAMA	Journal of the American Medical Association
LRTI	Lower Respiratory Tract Infection
MOP	Manual of Procedures
N	Number (typically refers to subjects)
NIAID	National Institute of Allergy and Infectious Diseases, NIH, DHHS
NIH	National Institutes of Health
OHRP	Office for Human Research Protections
PI	Principal Investigator
PCT	Procalcitonin
RADAR	Response Adjusted for Days of Antibiotic Risk
SAE	Serious Adverse Event
UADE	Unanticipated Adverse Device Effect
VAMC	Veterans Affairs Medical Center

## Protocol Summary

**Title:** Targeted Reduction of Antibiotics Using Procalcitonin in a Multi-center, Randomized, Double-Blinded, Placebo-Controlled Non-Inferiority Study of Azithromycin Treatment in Outpatient Adults with Suspect Lower Respiratory Tract Infection (LRTI) and a Procalcitonin (PCT) Level of  $\leq 0.25$  ng/mL (TRAP-LRTI)

**Phase:** Not Applicable, IDE

**Population:** Approximately 560 evaluable, adult subjects, presenting as outpatients with suspected LRTI with a PCT level of  $\leq 0.25$  ng/mL. In order to achieve this number of evaluable subjects, up to 840 will be enrolled.

**Number of Sites:** 6

**Study Duration:** Approximately 36 months

**Subject Participation Duration:** Approximately 28 days

**Description of Agent or Intervention:** Diagnostic Device: VIDAS® 3 platform and VIDAS® B.R.A.H.M.S Procalcitonin (PCT) test

Study Drugs: Azithromycin and placebo

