## 5 STUDY ENROLLMENT AND WITHDRAWAL

The study will recruit potential subjects 18 years of age or older who are suspected to have LRTI. In order to meet the primary objective, the study requires 560 evaluable subjects (approximately 280 per group). Taking into account subjects who withdraw, fail to complete Visit 3, or do not meet other inclusion criteria for the ATP population at Day 5 as defined in Section 11.4, this study will randomize approximately 674 enrolled subjects (approximately 337 per group) with PCT  $\leq 0.25$  ng/milk. Potential subjects will be recruited from hospital-based outpatient settings including EDs and clinics within our study sites in North Carolina (Duke University Hospital, Durham VA Medical Center), Georgia (Emory University Hospital and Atlanta VA Medical Center), New York (University of Rochester) and Texas (Houston VA Medical Center).

Clinical research personnel will approach patients meeting the clinical criteria (see inclusion criteria below) to discuss the study with them. Those who agree to participate will be consented for study enrollment and for future use samples. Declination to participate in collection of future use samples will not affect participation in the primary study. All enrolled subjects will have samples obtained including blood for PCT measurements and nasopharyngeal swabs for etiology testing. Subjects with a PCT  $\leq 0.25$  ng/mL will be randomized 1:1 to receive oral azithromycin or placebo.

Subjects with a PCT  $> 0.25$  ng/mL will not be randomized and will not receive study treatment. These subjects will have their charts reviewed for roughly 28 days after enrollment. Providers will be notified that the patient will not be randomized and therefore, the treating provider should make treatment decisions.

This type of consenting ensures that only patients who are willing to proceed to randomization and subsequent study activities are screened for PCT levels. Potential subjects will be identified at any time following clinical diagnosis of LRTI. Other forms and/or mechanisms of recruitment may also be used. The local IRB will approve recruitment materials prior to use.

A study clinician licensed to make medical diagnoses must confirm the subject meets Inclusion and Exclusion Criteria. No exemptions are granted on Subject Inclusion/Exclusion Criteria in DMID-sponsored studies. Questions about eligibility will be directed toward the DMID Medical Officer.

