## **5.4 Treatment Assignment Procedures**

### **5.4.1 Randomization Procedures**

Per International Council on Harmonisation (ICH) guideline E6: Good Clinical Practice (GCP), screening records will be kept at each participating site to document the reason why an individual was screened, but failed trial entry criteria. The reasons why individuals failed screening will be recorded on screening logs maintained by each site. Once consented and upon entry of demographic data and confirmation of eligibility for this trial, the subject will be enrolled. Only if the PCT is confirmed to be  $\leq 0.25$  ng/mL, will the subject be randomly assigned to 1 of 2 groups (1:1 ratio) to receive either azithromycin or placebo. Subjects with a PCT  $> 0.25$  ng/mL will remain enrolled but will not be randomized to receive study drug.

Enrollment of subjects will be performed online using AdvantageEDC. Lists of randomized treatment assignments will be prepared by statisticians at The Emmes Corporation and included

in The Emmes Corporation's Internet Data Entry System (IDES). IDES will assign each randomized subject a treatment code from the list after the necessary data has been entered into the system. Each site will have a supply of bottles pre-labeled with treatment numbers. Once a participant is assigned a treatment number, the corresponding bottle will be distributed to the participant. An unblinded pharmacist at each site will be provided with a treatment key, which links the treatment code to the actual treatment assignment, which will be kept in a secure place. Subjects will be stratified by site.

Instructions for subject enrollment are included in the Manual of Procedures (MOP). Manual back-up randomization procedures are provided in the MOP for use in the event that the site temporarily loses access to the Internet or the online enrollment system is unavailable.

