4.3. Selection of Study Population

The study will recruit potential subjects 18 years of age or older who are suspected to have LRTI. Subjects will be enrolled and randomized until the target sample size of 420 subjects (approximately 210 per group) is randomized in the PCT ≤ 0.25 ng/mL cohort. It is expected 50% of subjects meeting other entry criteria will have a PCT level of ≤ 0.25 ng/mL (based on the assumption that approximately 50% of patients with LRTI will have a PCT ≤ 0.25 ng/mL). Therefore, it is anticipated up to 840 subjects will be approached and enrolled to randomize 420 in the PCT level ≤ 0.25 ng/mL cohort to either azithromycin or placebo. Potential subjects will be recruited from hospital-based outpatient settings including EDs and clinics within our study sites in North Carolina (Duke University Hospital, Durham VA Medical Center), Georgia (Emory University Hospital and Atlanta VA Medical Center), and Texas (Houston VA Medical Center).

A study clinician licensed to make medical diagnoses must confirm the subject meets Inclusion and Exclusion Criteria. No exemptions are granted on Subject Inclusion/Exclusion Criteria in DMID-sponsored studies. Questions about eligibility will be directed toward the DMID Medical Officer.

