5. SAMPLE SIZE CONSIDERATIONS

The null hypothesis corresponding to the primary analysis if this study is:

Null hypothesis: $\pi_{\text{placebo}} - \pi_{\text{azithromycin}} \leq -12.5\%$,

Alternative hypothesis (non-inferiority): $\pi_{\text{placebo}} - \pi_{\text{azithromycin}} > -12.5\%$,

where π represents the probability of clinical improvement at study day 5. 12.5% is the non-inferiority margin used for this study.

The study was first designed assuming that 840 subjects would have to be enrolled in order to randomize 420 (50%) subjects and have 80% power to rule out a 12.5% increase in the clinical improvement rate with antibiotic therapy compared to placebo assuming a clinical improvement rate of 80% in each group using a two-sided 95% confidence interval (CI) using normal approximation with continuity correction with continuity correction, in the according-to-protocol analysis population at D5V (ATP-5) as defined in Section 6.3 (i.e., allowing for 15% loss in each treatment group).

These assumptions underlying the original target sample size of 420 subjects were assessed by a planned, interim, blinded analysis after approximately 210 subjects completed or terminated from the study. The interim report was finalized on January 9th, 2020. The observed clinical improvement rate at the time of the interim analysis was 57.6% in each group which is lower than the initially assumed 80% rate. Due to this finding, new sample size estimates have been generated to account for actual observed rates of clinical improvement and protocol deviations that preclude inclusion in the primary analysis. The total sample size was increased to enroll 674 subjects which will allow 560 subjects eligible for the ATP-5 analysis population allowing for 16.9% loss in each treatment group to follow up/rescue medication. This new sample provides 80% power to rule out a 12.5% increase in the clinical improvement rate with antibiotic therapy compared to placebo assuming a clinical improvement rate of 57.6% in each group using a two-sided 95% CI with continuity correction, in an according-to-protocol analysis (i.e., allowing for 16.9% loss in each treatment group to follow up/rescue medication).

Although analysis using an ATP population was used for determination of sample size (to account for missing data), the primary analysis will be an ITT analysis using all randomized subjects.

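### The enrolment figure of 840 has no stated basis at the new target of 674 randomised; at the only low-PCT rate printed (50%) it would yield 420

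*Protocol*

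**What the plan says.** The Protocol Summary sets a target of about 560 evaluable subjects and continues: "In order to achieve this number of evaluable subjects, up to 840 will be enrolled". Protocol section 5 gives the step in between: "this study will randomize approximately 674 enrolled subjects (approximately 337 per group"), and section 11.2 repeats 674 randomised for 560 in the ATP-5 population, allowing 16.9% loss.

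The SAP shows where 840 came from. Section 5: "The study was first designed assuming that 840 subjects would have to be enrolled in order to randomize 420 (50%) subjects". Section 4.3 gives the reason, "It is expected 50% of subjects meeting other entry criteria will have a PCT level of" 0.25 ng/mL or less, and still carries the original targets: "it is anticipated up to 840 subjects will be approached and enrolled to randomize 420 in the PCT level" cohort of 0.25 ng/mL or less. SAP sections 5 and 6.6 then report the re-estimation after the blinded interim analysis, which raised the randomised number from 420 to 674. Neither section gives a new enrolment figure.

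Enrolled and randomised are different counts. Under Protocol section 5.4.1, a consented and eligible subject is enrolled before the PCT criterion is applied, and a subject with PCT above 0.25 ng/mL "will remain enrolled but will not be randomized to receive study drug".

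**The concern.** The randomised target went up by 60% (674/420 = 1.60), while the enrolment figure meant to deliver it stayed the same. Since 840 was exactly 420 divided by 50%, it can serve 674 only if the low-PCT fraction is far above the original assumption. That fraction was one of three quantities the interim analysis was set up to assess (Protocol section 11.3.2; SAP sections 6.2 and 6.6). The SAP prints the other two revised values, 57.6% improvement and 16.9% loss, but no low-PCT fraction.

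At stake is whether the sample size can be reached within the stated enrolment. If 840 is treated as a maximum and the low-PCT fraction is well below 80%, the trial falls short of 674 and of its stated power. If sites recruit until 674 are randomised, enrolment goes beyond a figure that the Protocol Summary presents as an upper limit.

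**Working it through.** **Inputs.** Enrolment up to 840 and 560 evaluable (Protocol Summary); 674 randomised, 16.9% loss, 57.6% improvement in each group, two-sided 95% confidence interval with continuity correction, 80% power (Protocol section 11.2); margin 12.5 points (Protocol section 11.1); original design of 420 randomised, 50% low PCT, 15% loss and 80% improvement (SAP sections 4.3 and 5).

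**Formulas.** Randomised = evaluable / (1 − loss). Enrolled = randomised / low-PCT fraction.

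**The plan's own figures.**
- Original: 420 × 0.85 = 357 evaluable. With 80% improvement and the usual continuity correction, 80% power needs 177 per arm (354 in total), so 357 is consistent. Then 420 / 0.50 = 840 exactly.
- Revised: 560 / (1 − 0.169) = 674.

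**840 enrolled at 50% low PCT.**
- Randomised: 840 × 0.50 = 420, which is 254 short of 674.
- Evaluable: 420 × 0.831 = 349, which is 211 short of 560. Even with no loss, 420 is below 560.
- Power at 349 evaluable (m = 174.5 per arm): SE = √(2 × 0.576 × 0.424 / 174.5) = 0.0529; (0.125 − 1/174.5) / 0.0529 − 1.96 = 0.29; power about 62%. Without continuity correction it is about 66%.

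**Enrolment needed for 674 randomised.** The documents give no observed fraction, so the rows other than 50% are an assumed range.

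| Low-PCT fraction | Enrolment needed | Randomised from 840 |
|---|---|---|
| 50% | 1,348 | 420 |
| 60% | 1,124 | 504 |
| 70% | 963 | 588 |
| 80% | 843 | 672 |
| 80.2% | 840 | 674 |
| 90% | 749 | 756 |

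Break-even: 674 / 840 = 80.2%.

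**Sensitivity to the continuity correction.** The usual correction (1/m) gives about 83% power at 560 evaluable, slightly above the stated 80%. A larger correction (2/m) needs 277 per arm, 554 in total, which is closer to the plan's 560; with it, power at 349 falls to about 57%. The 62% is therefore not the least favourable choice.

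**The case against.** The strongest reply is that 840 may be right. The Protocol Summary entry was revised after the interim analysis, since it carries the new 560, and that analysis looked at the low-PCT fraction. Had the fraction been about 80%, the need would be 843, and keeping 840 would be reasonable. The 50% is a pre-interim planning value that appears only in the SAP. This stands: a reader might infer that 840 was simply forgotten, and the documents do not show that. They show an unchanged number with no stated basis.

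A reader might also infer that recruitment would stop near 420 randomised. That is not supported either. Protocol sections 5 and 11.2 set the target by number randomised and give no rule to stop at 840. SAP section 4.3 enrols until the randomised target is met and calls 840 only anticipated. The upper limit is worded as such in the Protocol Summary alone.

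The word enrolled is also used loosely. SAP section 5 says that 674 are to be enrolled where section 6.6 says randomised, and footnote 2 of Protocol Appendix A speaks of low-PCT subjects being enrolled and randomised. Section 5.4.1 is explicit, however, that high-PCT subjects remain enrolled. If 840 instead meant low-PCT subjects only, it would disagree with 674 and still need explaining.

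Finally, the primary analysis is ITT with imputation, whereas 62% is on the ATP-5 basis. That basis is the one on which the plan computes its own power. If all 420 randomised subjects were counted as fully observed, power would be about 70%, still below 80%.

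**Conclusion.** The point holds as an inconsistency between stated figures. At the only low-PCT rate in the documents, 840 enrolled cannot give 674 randomised or 560 evaluable: it gives 420 and about 349, with about 62% power on the ATP-5 basis, and 1,348 enrolled would be needed. The figure is adequate only at a low-PCT fraction of 80.2% or more, which neither document states.

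The calculation rests on high-PCT subjects counting as enrolled, 16.9% loss, 57.6% improvement in each group, and every low-PCT subject being randomised. Protocol section 4 allows a qualifying subject to decline randomisation, so the enrolment numbers above are minima.

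It does not show that the trial is infeasible or underpowered. The consequence depends on the unreported fraction and on how 840 is treated: a shortfall if it is a maximum, or enrolment beyond the stated maximum if recruitment follows the number randomised. The targets of 674 and 560 are not in question here.

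**What to change.** - Protocol Summary: print the low-PCT fraction observed at the interim analysis and restate enrolment as 674 divided by it. Keep 840 only if the fraction was about 80%, and say so.
- SAP section 4.3: replace the superseded 420, 50% and 840 with the same current figures.
- SAP section 5: in the sentence on the increased total, say that 674 are randomised, not enrolled, to agree with SAP section 6.6 and Protocol section 11.2.

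The cost is a few corrected figures in two documents. The fraction was part of the interim assessment, so no new data should be needed. The number randomised, the endpoint and the analysis stay as they are.

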### Objectives:

**Primary:**

- To compare the efficacy of azithromycin versus placebo on Day 5 (i.e., after 4 days of treatment) in subjects with suspect LRTI and PCT levels of  $\leq 0.25$  ng/mL at enrollment using a non-inferiority approach.

**Secondary:**

- To compare groups receiving azithromycin versus placebo with regard to all antibiotic use by Days 11 and 28.
- To compare groups receiving azithromycin versus placebo with regard to return visits to a physician's office or urgent care by Days 11 and 28.
- To compare groups receiving azithromycin versus placebo with regard to emergency department visits by Days 11 and 28.

- To compare groups receiving azithromycin versus placebo with regard to hospitalization by Days 11 and 28 if not hospitalized at the enrollment and randomization visit.
- To compare groups receiving azithromycin versus placebo with regard to improvement in presenting symptoms by Days 11 and 28.
- To compare the efficacy of azithromycin versus placebo on Day 11 in subjects with suspect LRTI and PCT levels of  $\leq 0.25$  ng/mL at enrollment using a non-inferiority approach.
- To compare the efficacy of azithromycin versus placebo on Day 28 in subjects with suspect LRTI and PCT levels of  $\leq 0.25$  ng/mL at enrollment using a non-inferiority approach
- To compare the efficacy of azithromycin versus placebo in subjects with suspected LRTI and PCT levels of  $\leq 0.25$  ng/mL at Day 5 using a superiority approach, employing the “Response Adjusted for Days of Antibiotic Risk (RADAR)” methodology.
- To compare groups receiving azithromycin versus placebo in regard to solicited events by Day 5.
- To compare groups receiving azithromycin versus placebo in regard to hospitalization or visits to an ED, outpatient clinic, or urgent care center for worsening or persistent LRTI after randomization by Day 5.
- To compare groups receiving azithromycin versus placebo in regard to improvement in vital sign abnormalities or symptoms present at enrollment, on Day 5.
- To compare groups receiving azithromycin versus placebo in regard to new vital sign abnormalities or symptoms on Day 5, or deterioration in symptoms relative to the enrollment visit on Day 5.

**Exploratory:**

- To compare PCT levels at Day 1 and Day 5 among treatment failures in the placebo and azithromycin groups
- To compare the efficacy of azithromycin versus placebo in subjects with suspected LRTI and PCT levels of  $\leq 0.25$  ng/mL at Day 11 using a superiority approach, employing the “Response Adjusted for Days of Antibiotic Risk (RADAR)” methodology
- To compare groups receiving azithromycin versus placebo in regard to solicited events by Day 11.
- To compare groups receiving azithromycin versus placebo in regard to hospitalization or visits to an ED, outpatient clinic, or urgent care center for worsening or persistent LRTI after randomization by Day 11.

- To compare groups receiving azithromycin versus placebo in regard to improvement in vital sign abnormalities or symptoms present at enrollment, on Day 11.
- To compare groups receiving azithromycin versus placebo in regard to new symptoms on Day 11, or deterioration in symptoms relative to the enrollment visit on Day 11.

[figure not shown]
**Description of  
Study Design:**

Double-Blind, Placebo-Controlled, Randomized, Non-Inferiority Trial

**Estimated Time  
to Complete  
Enrollment:**

36 months

## 2 BACKGROUND INFORMATION AND SCIENTIFIC RATIONALE

### 2.1 Background Information

Inappropriate prescribing of antibacterials for viral acute respiratory infection (ARI) contributes to increased healthcare costs, unnecessary drug-related adverse effects, and is a major contributor to antimicrobial resistance (1-5). Oral antibiotics have been attributed to ~20% of Emergency Department (ED) visits for drug-related adverse effects, mostly due to allergic reactions (6). In addition, the Centers for Disease Control and Prevention (CDC) recently reported ~23,000 deaths annually in the US due to multidrug resistant organisms. Antimicrobial stewardship programs have proven effective in driving more appropriate antibiotic use in inpatient settings where tight control, mandatory education, and feedback are available. However, most inappropriate antimicrobial use occurs in patients with ARIs (7-9). These are among the reasons why developing improved diagnostics that can be applied in the outpatient setting has been recommended by numerous entities including the Presidential Advisory Council on Combating Antibiotic-Resistant Bacteria.

In the most general terms, infection represents a maladaptive interaction between pathogen and host that manifests in clinical disease. However, those outward manifestations (e.g., fever, cough, malaise) are non-specific. Identifying the cause of these non-specific symptoms has largely focused on pathogen identification. While important, this approach has limitations including issues related to low sensitivity, low specificity, inability to distinguish infection from colonization, sampling error, and delays between testing and results (10). Different pathogen identification strategies overcome some but not all of these limitations. As a complement to current pathogen-focused testing, host-based biomarkers can provide useful diagnostic information. This is predicated on the observation that patients respond differently to viral and bacterial infection. No biomarker has received more attention in this regard than procalcitonin (PCT).

PCT was first described in the setting of sepsis, where concentrations were increased compared to non-infectious conditions (11). Moreover, PCT has been used to distinguish bacterial from viral infection because interferon gamma production induced by viral infections inhibits PCT production (12). As a result, PCT-guided management of LRTI (including COPD exacerbation and pneumonia) has been used to withhold antibiotics or shorten the duration of antibiotic therapy without adversely affecting outcomes in several European studies (13-15). Specifically, low PCT values ( $\leq 0.25$  ng/mL) were used to generate recommendations that antibacterials be withheld. Conversely, high PCT values prompted recommendations that antibacterials be provided. The results of these various studies are highlighted in a Cochrane database systematic review and showed that antibacterial use decreased by 50% without adversely affecting clinical outcomes (16).

This placebo-controlled, randomized, double blinded study represents an approach to the evaluation of PCT in LRTI that has not previously been evaluated. Based on the above evidence, we hypothesize that patients with suspected LRTI and a PCT value,  $\leq 0.25$  ng/mL, are unlikely to have a bacterial infection, and hence, will not benefit from antibacterial therapy. Therefore, treatment of these patients with placebo will be non-inferior to antibacterial therapy.

